9.2 Pathology

If a patient was confirmed at Roswell Park or an outside institute for CD20-positive DLBCL, then the diagnosis will be confirmed by centrally reviewing the available pathology material or the outside material utilized for this purpose. If confirmation is needed on outside material, a representative block or 15 unstained 4 μ m sections on 15 charged slides will be requested for this purpose.

Immunohistochemistry (IHC) will be utilized, if not already performed, to confirm the diagnosis of DLBCL and subtype it as Germinal Center (GC) or non-GC-like based on variable expression of CD10, BCL6, and MUM1 (based on Hans algorithm). Additional IHC markers that could be used, most of which are part of routine standard of care work up, include but not restricted to CD20, BCL1 (to exclude mantle cell lymphoma), BCL2, and ki-67.

A fresh lymph node/tumor biopsy needs to be repeated only for diagnostic purposes or if the patient has received additional chemotherapy after their previous biopsy. Fresh tissue or paraffin imbedded/unstained slides (N=15) (For Network Institutions) will be submitted to the department of pathology for standard and research protocol work-up. The tissue will be divided into standard of care diagnostic tissue (for H-E and IHC work-up, among others if needed such as flow cytometry immunophenotypic analyses and cytogenetics) and fresh tissue sent to Roswell Park Department of Medicine Lymphoma/Myeloma Laboratory (if sufficient tissue). Contact [name] at [contact] or [contact] for additional information.

Outside material should be sent to [name], Pathology Department, Roswell Park Comprehensive Cancer Center, [name], [name].

9.3 Immune Biomarker Blood Sample Collection

If the patient is undergoing a fresh lymph node/tumor biopsy, the following samples will be collected. Samples of blood will be collected using (5) 10 mL green-top heparinized tubes (1 tube for phenotype in flow cytometry, and 4 tubes for CMC/ADCC), (1) gold-tube (for CMC), and (1) 10 mL lavender-top tube (for genotypic analysis). Samples will be collected on the same day as the lymph node biopsy. Network Sites will collect immune biomarker samples on day of tumor biopsy if it is after the informed consent. Fresh tissue will not be collected from Network Sites.

One green top tube will be sent to the flow cytometry department and the remainder of the samples will be sent to Roswell Park Department of Medicine Lymphoma/Myeloma Laboratory for processing: Tube station #621 in Roswell Park Cancer Cell Center.

For additional information regarding the handling of samples please contact [name] at [contact] or [contact].

Refer to **Section 14.1** for analysis details.

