- 13 Repeat as medically indicated if positive at baseline.
- 14 Document absence of disease at least once in CR if previously involved.
- 15 At the time of relapsed/refractory disease diagnosis.
- 16 If the patient is undergoing a pre-treatment fresh biopsy - collect tissue with a goal of at least 0.5 g (in saline or media (RPMI 1640) provided to pathology by Roswell Park Department of Medicine Lymphoma/Myeloma Laboratory; fresh tissue will not be collected from Network Sites
- 17 Repeat diagnostic lymph node/tumor biopsy if initial biopsy was not diagnostic. Do not repeat due to less than 0.5g of tissue being collected.
- 18 Refer to Section 9.3. To be drawn the day of the tissue biopsy.
- 19 Refer to Section 9.4 PK [pharmacokinetics] and 14.2 PD pharmacodynamics)[proteasome inhibition]Cycle 1 only
- 20 As per BMT services
- 21 BM biopsy and aspiration to be completed within 28 days prior to enrollment
- 22 If biopsy is completed at an outside facility or Network Site, a tissue block or slides will be submitted to the Roswell Park Pathology Department for central pathology review. In addition immunohistochemistry (IHC) for CD20, Ki67, CD10, Bcl-2, Bcl-6, and MUM-1 staining will be performed. Cell of origin will be determined according to the Han's algorithm as previously described. Samples may only be shipped to Roswell Park Monday-Thursday.
- 23 For patients within the first 3 years of follow up, CT scans will be ordered every other visit. Patients on annual follow up will receive a CT scan at every study visit until the end of year 5, then CT scans will be ordered as clinically indicated
- 24 PK/PD samples will be collected in Phase 1 only

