14 CORRELATIVE STUDIES

14.1 Immune Biomarker Analysis

14.1.1 Blood

- Phenotypic Studies by direct flow cytometric analysis of neutrophils, NK and monocytes for the expression of CD11b/CD18; CD32, CD33, CD62, CD64, CD69, and

CD56 vFunctional Assays in vitro. (1) 10 ml green top – same day as lymph node biopsy

- Antibody-dependent cellular cytotoxicity (ADCC) assays: The capacity to lyse autologous tumor cells in the presence of RITUXAN by peripheral blood mononuclear cells of each patient will be studied by standardized assays, including appropriate controls. (4) 10 ml green tops – same day as lymph node biopsy
- Complement mediated cytotoxicity (CMC) assays: The capacity to lyse autologous tumor cells in the presence of RITUXAN by serum from each patient will be studied by standardized assays, including appropriate controls. (1) gold top – same day as lymph node biopsy
- Genotypic Analysis: Polymorphisms in the IgG Fc receptor FcγIIIa gene will be performed using a nested PCR followed by allele-specific restriction enzyme digestion performed in Roswell Park Department of Medicine Lymphoma/Myeloma Laboratory.(1) 10 ml lavender top – same day as lymph node biopsy
- Assay for proteasome inhibition of patient-derived primary DBLCL cells and PBMCs will be performed using an enzymatic assay for chymotrypsin-like activity. (1) 10 ml green top with each designated time point in Cycle 1 (see section 14.2)

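### The Fc-gamma receptor IIIa genotype tube is drawn only on the day of a fresh biopsy, so patients who enter on existing pathology material without a new biopsy go ungenotyped

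*Combined protocol and SAP*

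**What the plan says.** Section 9.3 opens the list of immune biomarker tubes with a condition: "If the patient is undergoing a fresh lymph node/tumor biopsy, the following samples will be collected". The list includes one lavender tube for genotyping. The same section fixes the timing: "Samples will be collected on the same day as the lymph node biopsy". For Network Sites it adds: "Network Sites will collect immune biomarker samples on day of tumor biopsy if it is after the informed consent".

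Two other places repeat the rule. Footnote 18 of the Study Calendar (Table 3, Section 9.1) reads: "Refer to Section 9.3. To be drawn the day of the tissue biopsy". The genotype bullet in Section 14.1.1 ("Polymorphisms in the IgG Fc receptor FcγIIIa gene will be performed using a nested PCR") gives the day of the lymph node biopsy as the time of the draw.

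Section 9.2 allows the diagnosis to be confirmed by central review of material already held, and says: "A fresh lymph node/tumor biopsy needs to be repeated only for diagnostic purposes". Its one further reason for a repeat is chemotherapy given since the previous biopsy. Footnote 17 agrees: a non-diagnostic biopsy is repeated, but a small tissue yield is no reason to repeat it.

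The genotype serves the correlative secondary objective in Section 3.3, which covers genotypic analysis of effector cells and an exploratory search for predictors of response.

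**The concern.** The biopsy condition suits some of the assays in the set but not the genotype. In Section 14.1.1 the ADCC and CMC assays measure lysis of the patient's own tumour cells, so drawing that blood with the tissue has a reason. The receptor polymorphism is read by PCR from blood. It is inherited, so the day of the draw does not matter to the result.

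A patient who enters on adequate existing histology, with no chemotherapy since, has no new biopsy and therefore no genotype. The loss is selective as well as avoidable: whether a patient is genotyped depends on diagnostic doubt, intervening chemotherapy and the type of site. Section 13.2 allows no imputation, so the predictor analysis would rest on whoever happened to be biopsied.

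**Working it through.** **Is there a fallback draw?** The plan states no sample size or precision for the genotype analysis, so there is no figure to reproduce. The check is of the sampling rule.

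- Section 9.3, footnote 18 and Section 14.1.1 all give the biopsy day. None gives a second time point.
- The calendar marks the immune biomarker samples in the column for Day 1 of each cycle, which could be read as a fallback. Its own footnote 18 sends the reader back to the biopsy day.
- The Cycle 1 proteasome-inhibition tubes (Sections 14.1.1 and 14.2) do not depend on a biopsy. They are not designated for genotyping, and footnote 24 limits them to Phase I.

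So there is no fallback, and the gap covers exactly the patients with no new on-study biopsy (at Network Sites, none after consent).

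**How many patients could a change reach?** Inputs: up to 21 Phase I and 9 Phase Ib patients, 30 in all (Sections 4.2 and 13.5.2). Section 4.1 already sets the Phase Ib dose from the Phase I results, so Phase I patients are taken to be past Cycle 1 Day 1. Let f be the share with a qualifying on-study biopsy, taken as equal in both parts. The documents do not give f.

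- Current rule: 30f genotyped.
- After the change: 21f + 9 genotyped.
- Gain: 9(1 − f).

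| f (assumed) | Current rule | After the change | Gain |
|---|---|---|---|
| 30% | 9 | 6.3 + 9 = 15.3, about 15 | 6.3 |
| 50% | 15 | 10.5 + 9 = 19.5, about 19 in whole patients | 4.5 |
| 100% | 30 | 21 + 9 = 30 | 0 |

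**What is that worth in precision?** For any proportion estimated in the genotyped set, the widest 95% half-width (normal approximation) is 1.96 × √(0.25/n):

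- n = 9: 0.327
- n = 15: 0.253
- n = 19: 0.225
- n = 30: 0.179

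At f = 30% the half-width falls from about 33 to 25 points; at f = 50%, from about 25 to 22. This is a scale only, because the plan does not set out to estimate a genotype frequency.

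**How far could the analysis go at best?** Suppose two equal genotype groups with response rates of 50% and 90% (an illustration) and a two-sided 0.05 test. Power is about 38% with 15 genotyped and 68% with all 30.

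**The case against.** The case for leaving the rule alone is that the genotype is one part of an exploratory objective, that the share biopsied is unknown and could be high, and that an amendment brings IRB review. All of that is true. It limits the benefit but supplies no reason for tying a blood genotype to a biopsy.

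The documents do not support four stronger readings that a reader might draw:

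- *Everyone whose relapse was already biopsied goes ungenotyped.* Patients re-biopsied for diagnosis or after further chemotherapy are sampled, subject to the consent condition at Network Sites.
- *Patients without a new biopsy give no biomarker blood.* In Phase I, proteasome-inhibition blood is drawn in Cycle 1 whether or not a biopsy is done.
- *The change would bring genotyping to all 30 patients, with the 18-point half-width.* Cycle 1 Day 1 has passed for Phase I. Catch-up draws would not repair this safely: under Section 10.4, patients who progress are followed for survival only, by records or telephone, so they have no routine study draw. Late samples would favour non-progressors and survivors, and missingness would then depend on the outcome being predicted.
- *The biopsy rule biases the genotype-response association.* The reasons for a new biopsy may relate to response, but nothing in the documents shows that they distort the association.

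The case is also weaker for the flow-cytometry phenotype tube. Drawing it on the biopsy day pairs it with the same-day ADCC and CMC assays, which is a plausible design choice.

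**Conclusion.** The point holds for the genotype tube: the sampling rule leaves some eligible patients ungenotyped with no scientific need, in a named secondary objective. It is a cheap improvement, not a flaw that threatens the trial. If 30-50% are biopsied on study, the change raises the number genotyped from about 9-15 to about 15-19 of 30, a gain of roughly four to six patients, all in Phase Ib. The gain shrinks to zero as the share approaches 100%. These figures rest on the assumed share, on its being equal in both parts, and on Phase I reaching its maximum of 21. Dose-limiting toxicity and response analyses are untouched, and the genotype analysis would remain exploratory even with every patient included.

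**What to change.** Amend Section 9.3, footnote 18 and the genotype bullet in Section 14.1.1 so that the lavender tube is drawn from every newly enrolled patient at the Cycle 1 Day 1 pre-dose blood draw, whether or not a biopsy is done. Make the calendar column and its footnote agree. Leave the ADCC and CMC tubes tied to the biopsy. The phenotype tube may be moved in the same way, as an option, provided it is drawn before the dexamethasone premedication that Section 8.1 places ahead of each carfilzomib dose.

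Do not rely on catch-up draws at later visits for the predictor-of-response analysis. If any are done, report them separately, with the number missing by response status.

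The cost is one 10 mL tube per patient at an existing draw, a few more in-house PCR tests, shipping from Network Sites, and an IRB-approved amendment with possible consent wording. No visit, biopsy or patient is added.

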9.4 Pharmacokinetic Blood Sample Collection and Processing (Phase 1 Only)

Whole blood samples for the pharmacokinetic analysis of carfilzomib levels will be collected via venipuncture using 4 mL green-top heparinized tubes.

PK samples will be collected pre-dose, just prior to the end of the infusion; and at 15 minutes, 30 minutes, 1, 2, 4, 6 hours post infusion on Cycle 1, Day 1, then at 24 hours post Cycle 1 infusion on Cycle 1, Day 2 (prior to Day 2 infusion).

PK samples will be sent to procurement lab. PD samples will be sent to Roswell Park Department of Medicine Lymphoma/Myeloma Laboratory for processing: Tube station #621 in Roswell Park Cancer Cell Center.

Plasma will be separated from the whole blood within 30 minutes following the extraction. The screw cap polypropylene cryogenic tube will be labeled with the subject's initials, subject's study number, clinical study number, protocol time point, dose, and protocol day. The samples will be frozen at -70°C or below until analyzed. After hours, samples will be processed in Lab Medicine.

The concentrations of carfilzomib in plasma will be determined using a validated LC/MS/MS method. Drug extraction will consist of protein precipitation with acetonitrile. The analytes will be separated on a C18 column with mobile phase consisting of acetonitrile, water and 0.1% formic acid. The method will be cross-validated before applying to the specimens for quantification. Quality assurance will be maintained by injecting quality control samples each time the samples are assayed.

Samples will be analyzed in Roswell Park Bioanalytics, Metabolomics & Pharmacokinetics Core Facility.

Roswell Park
Bioanalytics, Metabolomics & Pharmacokinetics Core Facility
Center for Genetics and Pharmacology, Room L1-140
Refer to Study Number – I 240813
[name]
[name]
[contact]

For additional information regarding the handling of pharmacokinetic samples please contact Roswell Park's Bioanalytics, Metabolomics & Pharmacokinetics Core Facility laboratory at [contact] (Tel) or [contact] (Fax).

Refer to **Section 14.2** for analysis details.

Note: All investigator or analyzing research laboratories housing research samples need to maintain current Temperature Logs and study-specific Sample Tracking and Shipping Logs. The Principal Investigator/Laboratory Manager must ensure that the stated lab(s) have a process in place to document the receipt/processing/storage/ shipping of study-related samples/specimens. This is required for both observational and interventional clinical studies collecting clinical samples.

10 EFFICACY EVALUATIONS

10.1 Objectives

One of the secondary objectives of this clinical study is to evaluate the overall response rate and complete response rate to C-R-ICE in rel/ref DLBCL. It is important to evaluate response to therapy using standardized response criteria utilized in previous clinical studies in DLBCL patients so direct comparisons can be performed with historical controls (i.e., R-ICE). For this reason response to therapy will be evaluated using the response criteria reported by Cheson published in 2007 which incorporate whole body PET scan in addition to CT scanning.

10.2 Imaging, Laboratory and Pathological Studies

Imaging, laboratory and pathological studies will be conducted for staging and response evaluation at baseline, between Cycle 2 Day 15 and Cycle 2 Day 28, and at the end of study evaluation following Cycle 3. Response to treatment will be evaluated according to the International Working Group Response criteria as reported by the revised Cheson criteria (Section 10.3).

10.3 Modified Cheson Criteria

10.3.1 Complete Response (CR)

- Complete disappearance of all detectable clinical evidence of disease and disease-related symptoms if present before therapy.
- Typically FDG-avid lymphoma: in patients with PET scan positive before therapy, a post-treatment residual mass of any size is permitted as long as it is PET negative.
- Variably FDG-avid lymphomas/FDG avidity unknown: in patients with a negative pretreatment PET scan, all lymph nodes and nodal masses must have regressed on CT to normal size (1.5 cm in their greatest transverse diameter for nodes 1.5 cm before therapy). Previously involved nodes that were 1.1 cm to 1.5 cm in their long axis and more than 1.0 cm in their short axis before treatment must have decreased to 1.0 cm in their short axis after treatment.
- The spleen and/or liver, if considered enlarged before therapy on the basis of a physical examination or CT scan, should not be palpable on physical examination and should be considered normal size by imaging studies, and nodules related to lymphoma should disappear. However, determination of splenic involvement is not always reliable because a spleen considered normal in size may still contain lymphoma, whereas an enlarged spleen may reflect variations in anatomy, blood volume, the use of hematopoietic growth factors, or causes other than lymphoma.
- If the bone marrow was involved by lymphoma before treatment the infiltrate must have cleared on repeat bone marrow biopsy.

- The bone marrow biopsy sample on which this determination is made must be adequate (with a goal of 20 mm unilateral core). If the sample is indeterminate by morphology, it should be negative by immunohistochemistry. A sample that is negative by immunohistochemistry but that demonstrates a small population of clonal lymphocytes by flow cytometry will be considered a CR until data become available demonstrating a clear difference in patient outcome.

10.3.2 Partial Response (PR)

- A decrease of $\geq 50\%$ in the sum of the products of their greatest transverse diameters (SPD) of the 6 largest dominant nodes or nodal masses. These nodes or masses should be selected according to the following features: a) they should be clearly measurable in at least two perpendicular measurements; b) they should be from as disparate regions of the body as possible; and c) they should include mediastinal and retroperitoneal areas of disease whenever these sites are involved.
- No increase in the size of other nodes, liver, or spleen.
- Spleen and hepatic nodules must regress by at least 50% in SPD.
- With the exception of splenic and hepatic nodules, involvement of other organs is considered assessable and not measurable disease.
- Bone marrow assessment is irrelevant for determination of a PR because it is assessable and not measurable disease; however, if positive the cell type should be specified in the report (e.g., large-cell lymphoma).
- Patients who achieve a CR by the above criteria, but who have persistent morphologic bone marrow involvement will be considered partial responders.
- When the bone marrow was involved before therapy and a clinical CR was achieved, but with no bone marrow assessment after treatment, patients should be considered partial responders.
- No new sites of disease should be observed.
- Typically FDG-avid lymphoma: for patients with no pretreatment PET scan or if the PET scan was positive before therapy, the post-treatment PET should be positive in at least one previously involved site.
- Variably FDG-avid lymphomas/FDG-avidity unknown: for patients without a pretreatment PET scan, or if a pretreatment PET scan was negative, CT criteria should be used.

10.3.3 Stable Disease (SD)

- A patient is considered to have SD when he or she fails to attain the criteria needed for a CR or PR, but does not fulfill those for progressive disease (see Relapsed Disease [after CR]/Progressive Disease [after PR, SD]).

- Typically FGD-avid lymphomas: the PET should be positive at prior sites of disease with no new areas of involvement on the post-treatment CT or PET.
- Variably FDG-avid lymphomas/FDG-avidity unknown: for patients without a pretreatment PET scan or if the pretreatment PET was negative, there must be no change in the size of the previous lesions on the post-treatment CT scan.

10.3.4 Progression (PD) or Relapse

- Lymph nodes should be considered abnormal if the long axis is more than 1.5 cm regardless of the short axis. If a lymph node has a long axis of 1.1 cm to 1.5 cm, it should only be considered abnormal if its short axis is more than 1 cm. Lymph nodes 1 cm x 1 cm will not be considered as abnormal for relapse or progressive disease.
- Appearance of any new lesion more than 1.5 cm in any axis during or at the end of therapy, even if other lesions are decreasing in size. Increased FDG uptake in a previously unaffected site should only be considered relapsed or progressive disease after confirmation with other modalities. In patients with no prior history of pulmonary lymphoma, new lung nodules identified by CT are mostly benign. Thus, a therapeutic decision should not be made solely on the basis of the PET without histologic confirmation.
- At least a 50% increase from nadir in the SPD of any previously involved nodes, or in a single involved node, or the size of other lesions (e.g., splenic or hepatic nodules). To be considered progressive disease, a lymph node with a diameter of the short axis of less than 1 cm must increase by 50% and to a size of 1.5 cm or more than 1.5 cm in the long axis.
- At least a 50% increase in the longest diameter of any single previously identified node more than 1 cm in its short axis.
- Lesions should be PET positive if observed in a typical FDG avid lymphoma or the lesion was PET positive before therapy unless the lesion is too small to be detected with current PET systems (1.5 cm in its long axis by CT).

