- Active CNS disease defined as symptomatic meningeal lymphoma or known CNS parenchymal lymphoma. A lumbar puncture demonstrating DLBCL at the time of registration to this study is not exclusion for study enrollment.

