- 3 Prior to study, at time of restaging; between Cycle 2 Day 15 to Cycle 2 Day 28 following Cycle 3 but before ASCT and at the end of treatment evaluation, then every 4 months (\pm 2 weeks) for 1 year, then every 6 months (\pm 2 weeks) for 2 years, then once a year (\pm 2 weeks) for 2 years for a total of 5 years, then as clinically indicated. The follow up period will begin at the end of study evaluation visit for patients that became ineligible for transplant for any reason but did not meet criteria for disease progression. The follow up period for patients that go on to transplant will begin at the Day +100 bone marrow biopsy.
- 4 At least every 4 months (\pm 1 week) for 1 year, then every 6 months (\pm 1 week) for 2 years, then once a year (\pm 2 weeks) for 2 years for a total of 5 years from study entry, then as clinically indicated. The follow up period will start at the Day 100 bone marrow biopsy in patients that received a transplant. Patients that progress will be followed for survival status only on a yearly basis.
- 5 If there is a greater than 10% difference in weight from baseline, then recalculate the BSA prior to each treatment; otherwise the actual dose given does not need to change.
- 6 CT Scan to be completed within 28 days prior to enrollment
- 7 When clinically appropriate.
- 8 CBC with differential and platelet counts will be monitored 3 times per week in between cycles of C-R-ICE until count recovery.
- 9 Days 1, 2, 8, and 9
- 10 All patients must be screened for hepatitis B infection (HBsAg/HBcAb) before starting treatment. Patients tested positive for HBV surface antigen are ineligible. Patients tested HBsAg negative/HBcAb positive should have qualitative HBV DNA PCR testing. If HBV DNA is positive the subject is excluded. If HBV DNA is negative, subject may be included but must undergo at least every 2 months HBV DNA PCR

testing from the start of treatment throughout the duration the treatment course. Monitoring during the on treatment periods is required at least every 2 months and during follow-up at a minimum of every 2 - 3 months up to 6 months after the last dose. Prophylactic antiviral may be initiated at the discretion of the investigator.

- 11 All patients must be screened for HCV infection before starting treatment. Patients who test positive for HCV antibody (Ab) evaluation of LFT's and clinical evaluation to rule out cirrhosis.
- 12 To be completed within 7 days prior to enrollment.

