10.3.5 Duration of Overall Response and/or Progression-Free Survival (in Non-Responders)

- The duration of overall response is measured from the time measurement criteria are met for CR/PR (whichever is first recorded) until the first date that recurrent or progressive disease is objectively documented (taking as reference for progressive disease the smallest measurements recorded since the treatment started).
- The duration of overall complete response is measured from the time measurement criteria are first met for CR until the first date that recurrent disease is objectively documented.
- Duration of Stable Disease

- Stable disease is measured from the start of the treatment until the criteria for progression are met, taking as reference the smallest measurements recorded since the treatment started.

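### Section 10.3.4 gives no explicit progression criterion for a new extranodal or CT-only lesion, or an isolated marrow or CSF relapse, first found in follow-up, so PFS and TTP may be biased upward

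*Combined protocol and SAP*

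**What the plan says.** Section 10.3.4 is the only place where the protocol sets out what counts as progression or relapse. Its new-lesion criterion is the "Appearance of any new lesion more than 1.5 cm in any axis during or at the end of therapy". Two further criteria concern growth of at least 50% in disease already known, with no time window. Three other statements in the section also carry no time window:

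- "Lymph nodes should be considered abnormal if the long axis is more than 1.5 cm regardless of the short axis"
- "Lymph nodes 1 cm x 1 cm will not be considered as abnormal for relapse or progressive disease"
- "Increased FDG uptake in a previously unaffected site should only be considered relapsed or progressive disease after confirmation with other modalities"

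Marrow and CSF do not appear in 10.3.4. Marrow is dealt with for CR (10.3.1) and PR (10.3.2). CSF is named in no response category.

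Section 8.4 caps treatment at three cycles, while Table 3 footnote 3 schedules disease evaluation for five years. For transplanted patients the same footnote says: "The follow up period for patients that go on to transplant will begin at the Day +100 bone marrow biopsy". Footnote 23 schedules follow-up CT at every other visit for three years and then at each annual visit to year 5. On CSF, Section 5.3 says: "A lumbar puncture demonstrating DLBCL at the time of registration to this study is not exclusion for study enrollment".

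Section 10.3.5 runs response duration "until the first date that recurrent or progressive disease is objectively documented" and ends CR duration in the same way at documented recurrence. Stable-disease duration ends when the progression criteria are met. TTP, PFS, OS and disease-free survival in CR patients are secondary objectives (Section 3.3). Section 13.5.3 plans Kaplan-Meier estimates of OS and PFS but lists no PFS events.

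**The concern.** Most of the observation time for PFS and TTP falls after therapy ends, yet the one criterion written for new lesions stops there. Marrow and CSF are sites that the protocol examines, and disease there is compatible with enrolment, but relapse in either has no rule.

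Read literally, a patient with such a relapse stays progression-free until known disease grows or another criterion is met. Read with judgement, one assessor counts the relapse and another does not. Follow-up is affected too: patients who progress move to yearly survival-only contact (Section 10.4; Table 3 footnote 4), so an unclassified relapse leaves it unclear which schedule applies.

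**Working it through.** **Text check.** Each kind of relapse is taken as first found in follow-up and compared with 10.3.4.

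| Finding in follow-up | What 10.3.4 offers | Status |
|---|---|---|
| Growth of known disease | 50% increase rules, no time window | Covered |
| FDG uptake at a previously uninvolved site, confirmed by another modality | FDG sentence, no time window | Covered |
| New node, long axis above 1.5 cm | Called abnormal; only 1 cm x 1 cm nodes are ruled out for relapse; no sentence makes it an event | Covered by inference |
| New extranodal lesion, or lesion seen on CT only | New-lesion bullet, limited to therapy and its end | No explicit criterion |
| Isolated marrow relapse | Nothing | No explicit criterion |
| Isolated CSF relapse | Nothing | No explicit criterion |

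The fourth row matters because Table 3 allows CT and/or PET, and footnote 23, which governs follow-up imaging, schedules only CT.

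**Which endpoints depend on 10.3.4.**

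- Stable-disease duration: explicitly, through 10.3.5.
- PFS and TTP: by implication, since neither has an event list and 10.3.4 is the only definition of progression.
- Response and CR duration: largely not, since 10.3.5 ends them at documented recurrence without limit of time or site.
- Primary response rate: not affected by the time limit, because it is assessed following Cycle 3, inside the window.

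**Illustration of direction.** The plan has no figure of its own to reproduce here. Inputs:

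- True 3-year PFS of 30%, borrowed from the background figure in Section 2.
- Uncounted share q of events, assumed to be 5% to 30%. The documents give no value.

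Model: exponential PFS, with uncounted events acting as independent censoring. The hazard is then multiplied by (1 − q), so apparent 3-year PFS = 0.30^(1 − q) and the median is multiplied by 1/(1 − q).

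| q | Apparent 3-year PFS | Median multiplied by |
|---|---|---|
| 5% | 0.30^0.95 = 31.9% | 1.05 |
| 10% | 0.30^0.90 = 33.8% | 1.11 |
| 20% | 0.30^0.80 = 38.2% | 1.25 |
| 30% | 0.30^0.70 = 43.1% | 1.43 |

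This shows the direction if events are missed. It does not show that any will be.

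**The case against.** The strongest reply is that the protocol plainly means relapse to count whenever it occurs. The section is headed for progression or relapse, most of its statements have no time window, and Section 10.4 speaks of progression at any time. Section 10.2 invokes the revised Cheson criteria, and a biopsy-proven marrow or CSF relapse is objective documentation under 10.3.5. Much of this stands. A reader might infer that no new-site relapse in follow-up meets any criterion. The documents do not support that, because the FDG sentence and, by inference, the nodal statements reach such relapses.

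The reply does not close the gap. Section 10.2 applies the Cheson criteria as set out in 10.3, and 10.3.5 says when recurrence is dated, not which findings constitute it. The nodal statements do not reach extranodal disease.

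The reply is also right that detection of marrow and CSF relapse is limited. Footnote 14 asks for marrow to document clearance at least once in CR if it was previously involved, and footnote 13 repeats lumbar puncture only on clinical need after a positive baseline. The Section 1.4.1 remark that carfilzomib does not cross the blood-brain barrier comes from animal toxicology and says nothing about how often CSF relapse would occur.

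**Conclusion.** The gap is real but narrow. A new extranodal or CT-only lesion, or an isolated marrow or CSF relapse, first found in follow-up has no explicit progression criterion. Applied literally, this may bias PFS, TTP and stable-disease duration upward. The documents do not allow the amount to be estimated; the range of 31.9% to 43.1% rests on an assumed share of 5% to 30%, a borrowed 30% and an exponential model with independent censoring.

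Three stronger readings are not supported:

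- **That PFS is overstated.** Assessors may count these relapses anyway, and PFS has no event list against which to demonstrate a bias.
- **That apparent 3-year PFS would be 37% to 51%.** With 30 × 0.70 = 21 events, shares of 10% and 30% leave 2.1 and 6.3 uncounted, giving (9 + 2.1)/30 = 37% and (9 + 6.3)/30 = 51%. This keeps every missed patient event-free to three years, with no later growth or death. It also applies the share to all 21 events, including any deaths and any progression on therapy.
- **That a planned comparison with the 30% PFS figure is compromised.** No such test is planned; 30% is background for patients who received salvage and transplant.

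The point concerns secondary endpoints. It deserves correction because a stated rule, followed as written, can give a wrong classification.

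**What to change.** Make three short edits:

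- In the new-lesion bullet of 10.3.4, replace the time limit so that a new lesion above 1.5 cm in any axis counts whenever it appears, on therapy or in follow-up.
- Add to 10.3.4 that new or recurrent lymphoma in marrow or CSF, confirmed by histology or cytology, is progression or relapse dated at the sample. Do not let a flow-only finding suffice: 10.3.1 accepts as CR a marrow that is negative by immunohistochemistry but shows a small clonal population by flow.
- State in 10.3.5 or 13.5.3 that PFS events are progression or relapse by 10.3.4, or death. The start date and censoring rule are also absent and belong in the same sentence.

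The cost is a few sentences. No new procedures are needed, since the rules use tests that the calendar already provides for. The downside is slightly less favourable PFS and TTP.
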